#### Clinical Laboratory Assessments

Clinical safety laboratory parameters evaluated after receipt of study product will include white blood cells (WBC), hemoglobin (HgB), platelets (PLT), alanine aminotransferase (ALT), aspartate aminotransferase (AST), alkaline phosphatase (ALP), total bilirubin (T Bili), creatine kinase (CK), and creatinine (Cr). These evaluations will be performed prior to vaccination and approximately 7 days after each study vaccination. Results will be graded using the FDA Toxicity Grading Scale for Healthy Adult and Adolescent Volunteers Enrolled in Preventative Vaccine Clinical Trials [4] and recorded by severity as mild/grade 1, moderate/grade 2, severe/grade 3, and potentially life threatening/grade 4, in addition to low (below normal range) and high (above normal range).

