## 9.6. Clinical Laboratory Evaluations

Chemistry parameters measured include alanine aminotransferase, aspartate aminotransferase, alkaline phosphatase, total bilirubin, creatine kinase, and creatinine. Hematology parameters measure include white blood cells, hemoglobin, and platelets.

Summaries of clinical laboratory data are grouped by vaccination arm, severity for each visit, and the maximum over all post-vaccination visits. Summaries are shown for each chemistry parameter and all chemistry parameters combined ([Table 312](#), [Table 313](#), [Table 314](#), [Table 315](#), [Table 316](#), [Table 317](#), and [Table 318](#)) and for each hematology parameter and all hematology parameters combined ([Table 325](#), [Table 326](#), [Table 327](#), and [Table 328](#)). Clinical laboratory results and change from baseline are also summarized by mean, standard deviation, median, minimum, and maximum for each chemistry parameter ([Table 319](#), [Table 320](#), [Table 321](#), [Table 322](#), [Table 323](#), and [Table 324](#)) and for each hematology parameter ([Table 329](#), [Table 330](#), and [Table 331](#)). Bar graphs of clinical laboratory results by maximum severity post baseline and vaccination arm will be presented [Figure 664](#), [Figure 665](#), [Figure 666](#), [Figure 667](#), and [Figure 668](#)).

Individual participant listings for abnormal chemistry results ([Table 310](#)) and abnormal hematology results ([Table 311](#)) will be presented.

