## 9.7. Vital Signs and Physical Evaluations

Vital signs including oral temperature, pulse, and systolic and diastolic blood pressure will be taken at each in-clinic visit. Vital signs assessed on Day 1 prior to the first study vaccination will be considered as baseline. Vital signs will be graded using the FDA Toxicity Grading Scale for Healthy Adult and Adolescent Volunteers Enrolled in Preventative Vaccine Clinical Trials [4] and recorded by severity as mild/grade 1, moderate/grade 2, severe/grade 3, and potentially life threatening/grade 4. Results will be tabulated by time point, severity, and vaccination arm for each vital sign and all vital signs combined ([Table 332](#), [Table 333](#), [Table 334](#), [Table 335](#), and [Table 336](#)).

Individual participant listings of vital signs will be presented ([Listing 14](#)).

A targeted physical examination may be performed, if indicated, based on review of interim medical history. Height and weight will be collected on Day 1 prior to the first study vaccination to calculate BMI, which will be presented with continuous demographics ([Table 42](#), [Table 43](#), [Table 44](#), [Table 45](#), and [Table 46](#)). Individual participant listings of physical exam findings will be presented ([Listing 15](#)).

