## 14.3 Safety Data

### 14.3.1 Displays of Adverse Events

**Table 212: Overall Summary of Adverse Events by Vaccination Arm – COVID-19 Vaccination Naïve, 18-60 years of age, Groups 1 and 3A**

Participants a with		Group 1: $5 \times 10^{10}$ vp ChAd-S/30 µg SAM-S (N=X)		Group 3A: 30 µg SAM-S/30 µg SAM-S (N=X)		All Participants (N=X)	
Category 1	Category 2	n	%	n	%	n	%
At least one local solicited adverse event	NA						
At least one systemic solicited adverse event	NA						
At least one unsolicited adverse event	NA						
At least one related unsolicited adverse event	Any Grade						
	Mild (Grade 1)						
	Moderate (Grade 2)						
	Severe (Grade 3)						
At least one severe (Grade 3) unsolicited adverse event	Any relationship						
Related	Related						
Unrelated	Unrelated						
At least one serious adverse event b	Any relationship						
	Related						
At least one adverse event leading to early termination c	NA						
At least one adverse event leading to treatment discontinuation	NA						
Any laboratory Adverse Event	NA						

Participants a with		Group 1: $5 \times 10^{10}$ vp ChAd-S/30 µg SAM-S (N=X)		Group 3A: 30 µg SAM-S/30 µg SAM-S (N=X)		All Participants (N=X)	
Category 1	Category 2	n	%	n	%	n	%
Any Vital Signs Adverse Event	NA						
At least one medically attended adverse event	NA						
At least one new onset chronic medical condition	NA						

N = Number of participants in the Safety Population  
aParticipants are counted once for each category regardless of the number of events.  
bA listing of Serious Adverse Events is included in [Table 307](#).  
cAs reported on the Adverse Event eCRF.

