**Table 308: Listing of Non-Serious, Unsolicited, Moderate or Severe Adverse Events**

Adverse Event	Associated with Dose No.	No. of Days Post Associated Dose (Duration)	Severity	Relationship to Study Treatment	If Not Related, Alternative Etiology	Action Taken with Study Treatment	Participant Discontinued Due to AE	Outcome	MedDRA System Organ Class	MedDRA Preferred Term
Participant ID: , Vaccination Arm: , AE Number:										
Comments:										
Participant ID: , Vaccination Arm: , AE Number:										
Comments:										

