### 14.3.5 Displays of Laboratory Results

#### 14.3.5.1 Chemistry Results

**Table 312: Laboratory Results by Parameter, Maximum Severity, Time Point, and Vaccination Arm – Any Chemistry Parameter**

Time Point	Vaccination Arm	N	None		Mild/ Grade 1 (Low)		Mild/ Grade 1 (High)		Moderate/ Grade 2 (Low)		Moderate/ Grade 2 (High)		Severe/ Grade 3 (Low)		Severe/ Grade 3 (High)		Missing	
			n	%	n	%	n	%	n	%	n	%	n	%	n	%	n	%
Baseline	Group 1: $5 \times 10^{10}$ vp ChAd/ 30 µg SAM-S	x	x	x	x	x	x	x	x	x	x	x	x	x	x	x	x	
	Group 3A: 30 µg SAM-S/ 30 µg SAM-S																	
	Group 3B: 30 µg SAM-S/ 3 µg SAM-S																	
	Group 4: 10 µg SAM-S-TCE/ 3 µg SAM-S-TCE																	
	Group 5: 3 µg SAM-S-TCE																	
	Group 6: 6 µg SAM-S-TCE																	
	Group 9: 3 µg SAM-S-TCE																	
	Group 10: 6 µg SAM-S-TCE																	
	Group 11: 10 µg SAM-S-TCE																	
	Group 13: $5 \times 10^{10}$ vp ChAd-S-TCE																	
	Group 14: $1 \times 10^{11}$ vp ChAd-S-TCE																	
	Group 15: $5 \times 10^{11}$ vp ChAd-S-TCE																	
All Participants																		

Time Point	Vaccination Arm	N	None		Mild/ Grade 1 (Low)		Mild/ Grade 1 (High)		Moderate/ Grade 2 (Low)		Moderate/ Grade 2 (High)		Severe/ Grade 3 (Low)		Severe/ Grade 3 (High)		Missing	
			n	%	n	%	n	%	n	%	n	%	n	%	n	%	n	%
Day 8	...																	
Day 29 (pre-dose 2 for Groups 1 and 3A)	...																	
Day 36 (8 days post-dose 2 for Groups 3A and 4)																		
Day 85 (pre-dose 2 for Groups 3B and 4)	...																	
Day 92 (8 days post-dose 2 for Groups 3B and 4)																		
Max Severity Post-Baseline	...																	

Note: The “Maximum Post Baseline” rows indicate the maximum severity experienced by each participant at any time point post baseline, including unscheduled assessments.  
N = Number of participants in safety population

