**Table 330: Laboratory Summary Statistics by Parameter, Time Point, and Vaccination Arm – Hemoglobin**

**Table 331: Laboratory Summary Statistics by Parameter, Time Point, and Vaccination Arm – Platelets**

### 14.3.6 Displays of Vital Signs

**Table 332: Vital Signs by Assessment, Maximum Severity, Time Point, and Vaccination Arm – Any Assessment**

Time Point	Vaccination Arm	N	None		Mild		Moderate		Severe		Missing	
			n	%	n	%	n	%	n	%	n	%
Baseline	Group 1: $5 \times 10^{10}$ vp ChAd/ 30 µg SAM-S	x	x	xx	x	xx	x	xx	x	xx	x	xx
	Group 3A: 30 µg SAM-S/ 30 µg SAM-S											
	Group 3B: 30 µg SAM-S/ 3 µg SAM-S											
	Group 4: 10 µg SAM-S-TCE/ 3 µg SAM-S-TCE											
	Group 5: 3 µg SAM-S-TCE											
	Group 6: 6 µg SAM-S-TCE											
	Group 9: 3 µg SAM-S-TCE											
	Group 10: 6 µg SAM-S-TCE											
	Group 11: 10 µg SAM-S-TCE											
	Group 13: $5 \times 10^{10}$ vp ChAd-S-TCE											
	Group 14: $1 \times 10^{11}$ vp ChAd-S-TCE											
	Group 15: $5 \times 10^{11}$ vp ChAd-S-TCE											
	All Participants											
Day 2												
Day 8	...											
Day 15												
Day 29	...											
Day 36	...											
Day 43	...											
Day 57	...											
Day 85												

Time Point	Vaccination Arm	N	None		Mild		Moderate		Severe		Missing	
			n	%	n	%	n	%	n	%	n	%
Day 86												
Day 92												
Day 99												
Day 113												
Day 169												
Day 181												
Day 209												
Day 265												
Day 366												
Day 394	...											
Day 450												
Max Severity Post Baseline	...											

Note: The “Max Post Baseline” rows indicate the maximum severity experienced by each participant at any time point post baseline, including unscheduled assessments.  
N = Number of participants in the safety population.

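### The SAP grades laboratory values and vital signs up to Grade 4, but all 16 by-arm severity tables stop at Grade 3 or Severe, so their maximum-severity rows cannot show the maximum

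*SAP*

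**What the plan says.** Section 4.5 (Clinical Laboratory Assessments) records post-vaccination laboratory results in four severity grades, the last two being "severe/grade 3, and potentially life threatening/grade 4, in addition to low (below normal range) and high (above normal range". Section 9.6 then sets out the tabulation: "Summaries of clinical laboratory data are grouped by vaccination arm, severity for each visit, and the maximum over all post-vaccination visits". It sends the chemistry summaries to Tables 312-318 and the hematology summaries to Tables 325-328.

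Section 9.7 grades vital signs on the same cited FDA scale and ends in the same way: "severe/grade 3, and potentially life threatening/grade 4. Results will be tabulated by time point, severity, and vaccination arm for each vital sign". These go to Tables 332-336.

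In Appendix 1, Table 312 gives the format for 313-318, Table 325 for 326-328, and Table 332 for 333-336. The last severity column in Tables 312 and 325 is "Severe/ Grade 3 (High"), and Missing follows it. Table 332, "Vital Signs by Assessment, Maximum Severity, Time Point, and Vaccination Arm – Any Assessment", has None, Mild, Moderate, Severe and Missing.

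For adverse events, Appendix 1 Section 12.2.2 says that all AEs and SAEs are graded on the same cited scale. The top severity row in Table 212 is "At least one severe (Grade 3) unsolicited adverse event". Section 9.3.2 promises a listing of non-serious events of moderate severity or above, while the shell is titled "Listing of Non-Serious, Unsolicited, Moderate or Severe Adverse Events".

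**The concern.** The text defines four grades and the tables meant to display them have room for three. No footnote says that Severe includes Grade 4, or that a column is added when one is needed. Safety and tolerability are the primary objective (Table 1), and these tables are how the plan summarises laboratory and vital-sign severity by arm.

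Platelets show what is at stake. Section 4.5 names TTS/VITT as an adverse event of special interest and makes platelets a graded safety parameter. A platelet count graded 4 (low) has no cell in Table 328, either at its visit or in the maximum-severity row.

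**Working it through.** No sample size, power or event figure is involved. The check sets the grades defined in the text against the columns in the shells.

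| Data | Grades in text | Tables | Severity columns in shell | Grade 4 column |
|---|---|---|---|---|
| Chemistry | 1-4, low/high (4.5) | 312-318 (7) | None; Grades 1-3 Low/High; Missing | none |
| Hematology | 1-4, low/high (4.5) | 325-328 (4) | None; Grades 1-3 Low/High; Missing | none |
| Vital signs | 1-4 (9.7) | 332-336 (5) | None; Mild; Moderate; Severe; Missing | none |

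Tables affected: 7 + 4 + 5 = 16. Tables with a Grade 4 column: 0 of 16. The maximum-severity rows use the same columns.

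**What can happen to one Grade 4 result.** In a row of N participants, the counts for None, each grade and Missing should add to N. Three outcomes are open to the programmer:
- The participant is omitted, and the row adds to N - 1.
- The participant is counted under Grade 3 or Severe. The row adds to N, but the top grade is understated.
- The participant is counted under Missing. The row adds to N, but an observed result is shown as absent.

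The SAP does not choose among these.

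**Share of an arm.** Table 2 gives 3 to 12 participants per enrolled arm. One participant is 1/12 = 8.3% to 1/3 = 33.3%. This is the weight of one person in a row, not an estimate of how often Grade 4 occurs.

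**Could the columns be meant as flexible?** Where the SAP wants a shell adapted, it says so. The note to Table 256 calls the organ classes examples, the note to Table 72 removes a row for D614G, and the note to Table 212 removes a row for Groups 5-15. The severity columns carry no such note.

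**Where Grade 4 can still appear.** Tables 310 and 311 list abnormal laboratory results with an open severity field. Listings 12-14 print the severity after each abnormal laboratory or vital-sign value. Tables 319-324 and 329-331 give the minimum and maximum of each laboratory parameter by arm and time point.

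**Size after the fix.** Each laboratory shell goes from 8 result columns (1 + 3 × 2 + 1) to 10 (1 + 4 × 2 + 1). Each vital-sign shell goes from 5 to 6.

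**The case against.** The strongest reply is that nothing is lost from the report. With 3 to 12 participants per arm, the by-participant tables and listings are a practical safety record, and they can show Grade 4. The laboratory summary-statistics tables would also show an extreme value. Section 1 calls the shells samples, and they appear to have been drafted with accrual known: Table 30 gives enrolment dates and Table 192 fills in arm sizes. An unused column may have been left out on purpose. If a Grade 4 value were counted as Severe, it would still sit at the highest level displayed.

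Much of this stands. A reader might infer that a Grade 4 result vanishes altogether; the listings rule that out. The explanation that the column was unused cannot be confirmed from the document, and listings do not repair a table whose purpose is to report the maximum.

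Three wider readings are also tempting and are not supported:
- **That the 56 adverse-event tables (212-216, 5; 256-306, 51) contradict the text in the same way.** Four grades are stated outright only for laboratory values and vital signs. For AEs they follow only from Section 12.2.2 pointing to the same guidance. A life-threatening AE is serious under Section 4.5 and has its own line in Table 307. The solicited-event tables stop at severe, in agreement with Section 9.3.1.
- **That vital signs lack a required Low/High split.** Section 9.7 promises no direction; Section 4.5 promises it for laboratory values only.
- **That dose escalation is compromised.** Section 4.1 gives that decision to the Study Steering Committee, with the DSMB consulted as needed, and Section 1 says that the shells are planned for the final analyses. Nor does the SAP describe the trial as first-in-human; it says phase 1.

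**Conclusion.** The contradiction is real and limited. Sections 4.5 and 9.7 define a Grade 4 that none of the 16 laboratory and vital-sign severity tables can display, and their maximum-severity rows fail at their one task if such a value occurs. The effect is confined to the aggregate by-arm summaries, because participant-level displays keep the grade. No estimate, analysis population or escalation decision is shown to depend on it.

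The conclusion rests on two assumptions: that the shells are programmed as drawn, and that the tables declared to have a similar format share the columns of the one shown. The severity bar charts (Figures 664-668) are not visible and were not assessed.

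The adverse-event shells and the title of Table 308 are secondary matters of consistency. For Table 308, Section 9.3.2 already states the wider inclusion rule, and the listing's severity field is open, so only the title is at odds.

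**What to change.** Add a Grade 4, potentially life-threatening column to Tables 312-318, 325-328 and 332-336, including their maximum-severity rows. Split it into Low and High for the laboratory parameters and leave it unsplit for vital signs. If no Grade 4 result occurred, keep the column at zero or say so in a footnote, so that the reader can tell no event from no cell.

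For consistency, reconcile Tables 212-216 and 256-306 with Section 12.2.2, either by adding the level or by stating how a Grade 4 event is displayed. Retitle Table 308 to match the moderate-or-greater rule in Section 9.3.2.

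The cost is shell edits and programming before the final tables are produced. No new data are needed, because Sections 4.5 and 9.7 already have the laboratory and vital-sign grades recorded.

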#### **Time Period and Frequency for Event Assessment and Follow-Up**

For this study, solicited adverse events will be collected for 7 days following each vaccine dose; unsolicited AEs will be collected until 28 days after each vaccination; AESIs (including PIMMCs, NOCMCs and MAAEs), SAEs, and AEs leading to withdrawal from the study will be collected from Day 1 through the end of the study. Clinical safety laboratory assessments are collected at Day 1 and 7 days post-vaccination for each dose.

## 5. SAMPLE SIZE CONSIDERATIONS

The targeted sample size for each of the study groups was determined based on previous phase 1 studies. The study is targeted to enroll up to 135 participants, with up to 12 participants in each group.

### Sample size calculations for safety

The goal of the safety evaluation for this study is to identify safety concerns associated with product administration. The ability of the study to detect SAEs (see Section 4.5) can be expressed by the true event rate above which at least 1 SAE would likely be observed and the true event rate below which no events would likely be observed in each of the groups.

Specifically, in each sentinel group of 3 participants, there is a 48.8% chance of observing at least 1 event if the true rate of such event is 20% or higher; and there is at least a 72.9% chance of observing no events if the true event rate is 10% or less. For each group of 7 participants, there is a 79% chance of observing at least 1 event if the true rate is 20% or higher, and there is at least 47.8% chance of observing no events if the true event is 10% or less. For each group of 10 participants, there is an 89.3% chance of observing at least 1 event if the true rate is 20% or higher, and there is at least 34.9% chance of observing no events if the true event is 10% or less. For each group of 12 participants, there is a 93.1% chance of observing at least 1 event if the true rate is 20% or higher, and there is at least 28.2% chance of observing no events if the true event is 10% or less.

Binomial probabilities of observing 0, 1 or more, and 2 or more events among groups of size 3, 7, 10 or 12 are presented in Table 4 for a range of possible true adverse event rates. These calculations provide a more complete picture of the sensitivity of the study design to identify potential safety problems with the vaccine.

**Table 4: Probability of observing 0 events, 1 or more events, and 2 or more events, among groups of size 3, 10, for different true event rates**

True Event Rate (%)	Group Size (N)	Pr(0 Events)	Pr(1+ Events)	Pr(2+ Events)
1	3	97	3	<0.1
	7	93.2	6.8	0.2
	10	90.4	9.6	0.4
	12	88.6	11.4	0.6
4	3	88.5	11.5	0.5
	7	75.1	24.9	2.9
	10	66.5	33.5	5.8
	12	61.3	38.7	8.1
10	3	72.9	27.1	2.8
	7	47.8	52.2	15
	10	34.9	65.1	26.4
	12	28.2	71.8	34.1
20	3	51.2	48.8	10.4
	7	21.0	79.0	42.3

True Event Rate (%)	Group Size (N)	Pr(0 Events)	Pr(1+ Events)	Pr(2+ Events)
	10	10.7	89.3	62.4
	12	6.9	93.1	72.5

### **Sample size calculations for SARS-CoV-2-specific antibody binding and neutralization titer in serum**

A secondary endpoint of this study is to evaluate the magnitude of SARS-CoV-2-specific antibody binding and neutralization titers in serum samples. This endpoint is descriptive in nature and will be accomplished by estimating the geometric mean titer (GMT) at each timepoint when samples are collected.

The precision with which a true GMT can be estimated from observed data depends on the standard deviation (SD) of the measurements, in the logarithmic scale, and the sample size. [Table 5](#) displays two-sided 95% confidence intervals for the GMT for several values of the observed antibody titer.

**Table 5: Two-sided 95% confidence intervals based on observing a particular average loge antibody titer in participants' groups, taking 0% or 20% attrition into consideration (n = 12, 10, 8, 7)**

Observed average log e antibody titer	SD of log e antibody titer	95% confidence interval			
		n=12	n = 10	n = 8	n=7
log e (5)	0.5	(3.6, 6.9)	(3.5, 7.2)	(3.3, 7.6)	(3.1,7.9)
log e (20)		(14.6, 27.5)	(14, 28.6)	(13.2, 30.4)	(12.6,31.8)
log e (50)		(36.4, 68.7)	(35, 71.5)	(32.9, 75.9)	(31.5,79.4)
log e (100)		(72.8, 137.4)	(69.9, 143)	(65.8, 151.9)	(63,158.8)
log e (250)		(182, 343.5)	(174.8, 357.5)	(164.6, 379.7)	(157.4,397)
log e (500)		(363.9, 687)	(349.6, 715)	(329.2, 759.5)	(314.9,794)
log e (1000)		(727.8, 1373.9)	(699.3, 1430)	(658.4, 1518.9)	(629.8,1587.9)
log e (5)	1.0	(2.6, 9.4)	(2.4, 10.2)	(2.2, 11.5)	(2,12.6)
log e (20)		(10.6, 37.8)	(9.8, 40.9)	(8.7, 46.1)	(7.9,50.4)
log e (50)		(26.5, 94.4)	(24.5, 102.2)	(21.7, 115.4)	(19.8,126.1)
log e (100)		(53, 188.8)	(48.9, 204.5)	(43.3, 230.7)	(39.7,252.1)
log e (250)		(132.4, 471.9)	(122.3, 511.2)	(108.4, 576.8)	(99.1,630.4)
log e (500)		(264.9, 943.9)	(244.5, 1022.5)	(216.7, 1153.6)	(198.3,1260.7)
log e (1000)		(529.7, 1887.7)	(489, 2044.9)	(433.4, 2307.2)	(396.6,2521.5)

## 6. GENERAL STATISTICAL CONSIDERATIONS

### 6.1. General Principles

Unless otherwise noted, continuous variables will be summarized using the following descriptive statistics: n (non-missing sample size), mean, standard deviation, median, maximum and minimum. The frequency and percentages (based on the non-missing sample size) of observed levels will be reported for all categorical measures.

### 6.2. Timing of Analyses

After the last participant completes their last visit and all data is received by the Statistical and Data Coordinating Center (SDCC), data cleaning and locking processes will be completed. The final analysis will be performed after data lock.

Prior to the final analysis, data may be disseminated to public health officials and partners as needed and included in publications and presentations to inform the global scientific community. Early analyses will include safety and immunogenicity. Further, the protocol team will review data periodically to confirm that no halting rules have been met as described in Section 8.6.1 of the protocol.

Cumulative safety information, study status, and endpoint results may be published, presented at a public forum, or presented as summaries aggregated by study arm at the discretion of the sponsor while the primary study is ongoing. Any ad hoc analyses, jointly developed by the protocol team, SDCC and/or Gritstone bio, Inc. (formerly known as Gritstone Oncology, Inc.), will be executed by the SDCC as needed. None of the interim analyses will include any formal statistical hypothesis testing.

